6.2.10 Revised Amyotrophic Lateral Sclerosis Functional Rating Scale (ALSFRS-R)

Subscore for Fine and Gross Motor Functions will be calculated as sum of scores for items 4 to 9; subscore for Bulbar Function will be calculated as sum of scores for items 1 to 3.

QMD Ref: Worldwide-TMP-ST-005-7.0 Effective: 12Aug2019	Governing QMD: Worldwide-SOP-ST-001
Confidentiality Statement	

This document is the property of Worldwide Clinical Trials Inc. and may not be duplicated, copied, altered or removed from company without prior approval from Worldwide Quality Assurance or in compliance with Worldwide Standard Operating Procedures.

Worldwide Clinical Trials Controlled Quality Management Document			
 WORLDWIDE CLINICAL TRIALS	Sponsor:	Helixmith Co., Ltd.	
Protocol Number:			VMALS-002-2
STATISTICAL ANALYSIS PLAN VERSION 3.0			

6.2.11 Amyotrophic Lateral Sclerosis Assessment Questionnaire (ALSAQ-40)

The questionnaire consists of 40 questions (Q1-Q40), which are converted to 5 subscales using the following rules (according to the ALSAQ User Manual):

PHYSICAL MOBILITY = $((Q1 + Q2 + Q3 + Q4 + Q5 + Q6 + Q7 + Q8 + Q9 + Q10)/40) \times 100$.

ACTIVITIES OF DAILY LIVING/INDEPENDENCE = $((Q11 + Q12 + Q13 + Q14 + Q15 + Q16 + Q17 + Q18 + Q19 + Q20)/40) \times 100$.

EATING AND DRINKING = $((Q21 + Q22 + Q23)/12) \times 100$.

COMMUNICATION = $((Q24 + Q25 + Q26 + Q27 + Q28 + Q29 + Q30)/28) \times 100$.

EMOTIONAL FUNCTIONING = $((Q31 + Q32 + Q33 + Q34 + Q35 + Q36 + Q37 + Q38 + Q39 + Q40)/40) \times 100$.

The following approaches will be used in case of missing or incorrectly filled questions:

- Worst values will be imputed
- Average value of correctly filled questions of the subscale

If a subscale of the questionnaire will have less than 50% correctly answered questions, it should be considered as missing.

Subscale values will be presented with 1 decimal place. Number of decimal places for descriptive statistics will be presented using rules in Section 6.3.1.

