6.15.4 Amyotrophic Lateral Sclerosis Assessment Questionnaire, 40 questions (ALSAQ-40)

ALSAQ-40 will be measured at Day 0 pre-dose, Day 84 and Day 180.

Values of each question and their changes from baseline will be presented with descriptive statistics for each visit by treatment group (Table 14.6.4.1 and 14.6.4.2, Listing 16.2.9.4).

The subscales (physical mobility, activities of daily living/independence, eating and drinking, communication, and emotional functioning) will be presented with descriptive statistics for values on each visit and changes from baseline for each post-baseline visit (Tables 14.6.4.3 and 14.6.4.4).

6.15.5 Clinical Global Impression of Change (CGIC) and Patient Global Impression of Change (PGIC)

QMD Ref: Worldwide-TMP-ST-005-7.0 Effective: 12Aug2019	Governing QMD: Worldwide-SOP-ST-001
Confidentiality Statement	

This document is the property of Worldwide Clinical Trials Inc. and may not be duplicated, copied, altered or removed from company without prior approval from Worldwide Quality Assurance or in compliance with Worldwide Standard Operating Procedures.

Worldwide Clinical Trials Controlled Quality Management Document			
 WORLDWIDE CLINICAL TRIALS	Sponsor:	Helixmith Co., Ltd.	
Protocol Number:			VMALS-002-2
STATISTICAL ANALYSIS PLAN VERSION 3.0			

CGIC and PGIC will be measured at Day 84 and Day 180.

CGIC (Global improvement and Efficacy index) and PGIC (Impression of change and Degree of Change) will be presented with descriptive statistics for each visit by treatment group (Tables 14.6.5 and 14.6.6, Listings 16.2.9.5 and 16.2.9.6).

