14.3.6.1	Vital Signs – Safety Analysis Population	IP	
14.3.6.2	Vital Signs, Patients with Clinically Significant Values – Safety Analysis Population	IP	
14.3.6.3	Physical Examination, Shift Table – Safety Analysis Population	IP	
14.3.7	Other Safety		
14.3.7.1	Electrocardiogram – Safety Analysis Population	IP	
14.3.7.2	Electrocardiogram, Shift Table – Safety Analysis Population	IP	
14.3.8	Concomitant Medication		
14.3.8.1	Prior Medications – Safety Analysis Population	IP	
14.3.8.2	Concomitant Medications – Safety Analysis Population	IP	14.3.8.1
14.4	PK Tables		
14.5	PD Tables		
14.6	Other Data		
14.6.1	Revised Amyotrophic Lateral Sclerosis Functional Rating Scale – ITT Population	IP	
14.6.2	Handheld Dynamometry – ITT Population	IP	
14.6.3	Accurate Test of Limb Isometric Strength – ITT Population	IP	14.6.2
14.6.4.1	Amyotrophic Lateral Sclerosis Assessment Questionnaire, 40 questions (worst values imputation) – ITT Population	IP	
14.6.4.2	Amyotrophic Lateral Sclerosis Assessment Questionnaire, 40 questions (average values imputation) – ITT Population	IP	14.6.4.1
14.6.4.3	Amyotrophic Lateral Sclerosis Assessment Questionnaire, subscales (worst values imputation) – ITT Population	IP	
14.6.4.4	Amyotrophic Lateral Sclerosis Assessment Questionnaire, subscales (average values imputation) – ITT Population		14.6.4.3

QMD Ref: Worldwide-TMP-ST-005-7.0 Effective: 12Aug2019

Governing QMD: Worldwide-SOP-ST-001

Confidentiality Statement

This document is the property of Worldwide Clinical Trials Inc. and may not be duplicated, copied, altered or removed from company without prior approval from Worldwide Quality Assurance or in compliance with Worldwide Standard Operating Procedures.

Worldwide Clinical Trials Controlled Quality Management Document			
 WORLDWIDE CLINICAL TRIALS	Sponsor:	Helixmith Co., Ltd.	
	Protocol Number:	VMALS-002-2	
STATISTICAL ANALYSIS PLAN VERSION 3.0			

Table Number	Table Title	Validation Method	Shell Number (if repeat)
14.6.5	Clinical Global Impression of Change – ITT Population	IP	
14.6.6	Patient Global Impression of Change – ITT Population	IP	
14.6.7	Slow Vital Capacity – ITT Population	IP	
14.6.8	Time to Tracheostomy – ITT Population	IP	
14.6.9	Time to All-Cause Mortality – ITT Population	IP	14.6.9

QMD Ref: Worldwide-TMP-ST-005-7.0 Effective: 12Aug2019	Governing QMD: Worldwide-SOP-ST-001
Confidentiality Statement	

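### The ALSAQ-40 question-level tables are planned only on imputed answers, and the SAP does not say whether its 50% rule reaches single questions

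*SAP*

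**What the plan says.** SAP 6.2.11 describes how the 40 questions become five subscales. For gaps it states: "The following approaches will be used in case of missing or incorrectly filled questions". Two approaches follow: "Worst values will be imputed" and "Average value of correctly filled questions of the subscale". It then sets a minimum amount of data: "If a subscale of the questionnaire will have less than 50% correctly answered questions, it should be considered as missing".

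SAP 6.15.4 plans output at two levels. For single questions: "Values of each question and their changes from baseline will be presented with descriptive statistics for each visit by treatment group", assigned to Tables 14.6.4.1 and 14.6.4.2 and Listing 16.2.9.4. The subscales have their own pair, Tables 14.6.4.3 and 14.6.4.4.

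Section 11 titles Table 14.6.4.1 "Amyotrophic Lateral Sclerosis Assessment Questionnaire, 40 questions (worst values imputation) – ITT Population". Table 14.6.4.2 has the same title with average-value imputation. No question-level table of the answers as given is listed. Listing 16.2.9.4 covers the 40 questions and carries no imputation label.

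**The concern.** Filling one item so that a ten-item sum can be formed changes a small part of the score. In a table of one question, the filled-in value is everything that participant contributes. The worst-value table then reports a maximum that nobody chose, and the average-value table reports a participant's answers to other questions as the answer to this one. SAP 6.3 reports the number of non-missing observations, so filled values would count in n and enter the mean, confidence interval and SD. This applies at every visit and to changes from baseline.

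The 50% rule does not clearly protect these tables. It sets the subscale to missing and says nothing about the questions inside it. A programmer could impute them or leave them blank, and both choices fit the text.

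With 6 Placebo and 12 Engensis participants, one filled value is a visible share of an arm mean.

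**Working it through.** **Inputs**
- Arm sizes: 12 Engensis and 6 Placebo (Protocol 5.3).
- Questions per subscale and divisors: SAP 6.2.11.
- Number of blanks: not given in either document. One blank per arm is assumed below for illustration.

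The plan states no figure on this point, so there is none to reproduce first.

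**Step 1. Item range.** Each divisor divided by its number of questions gives the highest item score: 40/10 = 4 (physical mobility, activities of daily living, emotional functioning), 12/3 = 4 (eating and drinking), 28/7 = 4 (communication). Items run 0 to 4, and the worst value is 4.

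**Step 2. When the 50% rule acts.** Fewer than half answered means:

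| Subscale size | Answered, at most | Blank, at least |
|---|---|---|
| 10 questions | 4 | 6 |
| 7 questions | 3 | 4 |
| 3 questions | 1 | 2 |

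From these counts the subscale leaves Tables 14.6.4.3 and 14.6.4.4. If the programmer still imputes the questions, each blank enters Table 14.6.4.1 as 4 and enters Table 14.6.4.2 as the mean of the answers given, which in eating and drinking can be a single answer. If no question of a subscale is answered, the average has no value and only the worst-value table could be filled. The SAP does not address that case either.

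**Step 3. Shift in a question mean, worst value against observed answers.** Let m be the mean of the answers actually given in the arm.
- Placebo, one blank of 6: (5m + 4)/6 − m = (4 − m)/6.
- Engensis, one blank of 12: (11m + 4)/12 − m = (4 − m)/12.

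| m | Placebo | Engensis |
|---|---|---|
| 0 | 4/6 = 0.67 | 4/12 = 0.33 |
| 1 | 3/6 = 0.50 | 3/12 = 0.25 |
| 2 | 2/6 = 0.33 | 2/12 = 0.17 |

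**Step 4. Illustration.** Placebo answers of 0, 1, 1, 2, 1 and one blank:
- Observed: n = 5, mean 5/5 = 1.00, SD 0.71.
- Worst value: n = 6, mean (5 + 4)/6 = 1.50, SD 1.38.
- Average value, if that participant's other answers in the subscale average 0.75: n = 6, mean 5.75/6 = 0.96, SD 0.64.

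Here the average rule barely moves the mean but adds one to n and lowers the SD.

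**Step 5. Change from baseline.** Take a participant whose true answer is 1 at both visits. A Day 180 blank set to 4 gives a change of 4 − 1 = +3; a baseline blank gives 1 − 4 = −3. If the others in the arm show no change on average, the mean change moves by 3/6 = 0.50 in Placebo or 3/12 = 0.25 in Engensis. The observed-answer table would omit this participant's change.

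**The case against.** **The recorded answers are reported.** SAP 6.3 says that all data will be listed, and Listing 16.2.9.4 covers the questions. This stands: with 18 participants a reader could find every blank. A reader might infer that the recorded answers are lost, and the documents do not support that. A listing still gives no summary by arm.

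**The two imputations are labelled and shown side by side.** Where nothing is blank they agree, so a discrepancy reveals imputation. This is fair, and it makes them usable as sensitivity displays. It does not supply the observed result to compare them with.

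**The 50% rule may reach the questions.** The imputation approaches and the rule appear together in a section about subscales, and table shells could settle it. This stands in part. It would go too far to say that the SAP requires imputing the questions of a subscale set to missing; it is silent.

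**The largest shift is tempting to quote alone.** The 0.67 for Placebo is reached only when the five other answers average 0. It also equals the error when the blank's true answer is 0, but an observed-answer table would not recover that 0. It omits the participant.

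**Observed answers carry an assumption too.** They describe only those who answered, and blanks in a progressive disease may be informative. SAP 6.2.11 refers to a user manual that is not available here. Both limits are accepted.

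**Blanks may be rare.** The questionnaire is collected electronically (Protocol 8.3.5.1), participants are trained (10.1.6.5) and asked to answer everything (Appendix 7), and missing data are raised with sites (10.1.6.3). This lowers the likelihood. The check for completeness before leaving the clinic is described for the PGIC (8.3.5.2), not for the ALSAQ-40.

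**Conclusion.** The point holds as a minor one. The question-level tables are planned only with imputed answers, and the SAP leaves open whether the 50% rule governs them. One blank set to the worst value raises a question mean, against observed answers, by (4 − m)/6 in Placebo or (4 − m)/12 in Engensis: 0.50 or 0.25 at m = 1, and at most 0.67 or 0.33. These figures assume full arms of 6 and 12 with one blank in the arm, and they apply to the worst-value table only.

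The consequence is limited. ALSAQ-40 is an exploratory endpoint, its planned output is descriptive, and the number of blanks is unknown. A reader might also see a conflict with the no-imputation statement in Protocol 9.3.1. There is none, because that statement concerns the safety analyses.

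**What to change.** 1. Present the 40 questions and their changes on observed answers, with n per question and visit. Tables 14.6.4.1 and 14.6.4.2 may be dropped, or kept as labelled sensitivity displays.
2. State in SAP 6.2.11 that imputation is used only to compute a subscale score, and only when at least 50% of that subscale's questions are answered (Tables 14.6.4.3 and 14.6.4.4, both kept).

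The cost is a change of SAP wording and of table specifications, with no new data. If both imputed question tables are replaced by the observed one, there is one table fewer. The downside is that n varies by question. Question and subscale tables may also still cover slightly different participants: someone answering 2 of the 3 eating and drinking questions has a subscale score but is absent from one question row, and someone answering 1 of 3 appears in one question row but has no subscale score.

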**8.3.4. Muscle Biopsies**

Helixmith intends to use muscle biopsy samples of the gastrocnemius to evaluate biomarkers in order to gain further understanding of Engensis' mechanism of action and muscle atrophy in ALS. Testing results could provide information for future uses of Engensis in ALS. A biopsy of the gastrocnemius will be collected (and stored) at Day 0 predose, and on Days 84 (optional) and 144. See the Muscle Biopsy Guidelines for detailed information on the techniques and procedures to be used.

**8.3.5. Quality of Life Assessment, Patient Reported Outcomes, and Clinical Reported Outcomes****8.3.5.1. Amyotrophic Lateral Sclerosis Assessment Questionnaire**

The Amyotrophic Lateral Sclerosis Assessment Questionnaire (ALSAQ-40) is a disease-specific, Participant self-report health status, or electronic patient-reported outcome (ePRO). There are 40 questions in the ALSAQ-40 with 5 discrete scales: physical mobility (10 questions), activities of daily living and independence (10 questions), eating and drinking (3 questions), communication (7 questions), and emotional reactions (10 questions). The ALSAQ-40 will be measured predose on Day 0 and at Visits on Days 84 and 180/ET. See Section 10.7, Appendix 7, for the ALSAQ-40 questionnaire.

Participants are asked to think about the difficulties that they may have experienced during the last two weeks (e.g., "I have found it difficult to feed myself"). Participants are asked to indicate the frequency of each event by selecting one of 5 options (Likert scale): never, rarely, sometimes, often, always, or cannot do at all.

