6.2.2 Baseline

Baseline for safety parameters as well as for exploratory parameters is defined as the last non-missing value (either scheduled, unscheduled or repeat) before the participant receives first Study Injection.

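### Worst-value imputation of ALSAQ-40 items is not excluded at the Day 0 baseline, where it can create apparent improvement, and neither imputation rule is named as the main one

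*SAP*

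**What the plan says.** SAP 6.2.11 introduces the handling of incomplete questionnaires with "The following approaches will be used in case of missing or incorrectly filled questions". It then lists two: "Worst values will be imputed" and "Average value of correctly filled questions of the subscale". No visit is mentioned and the two are not ranked. One limit follows: "If a subscale of the questionnaire will have less than 50% correctly answered questions, it should be considered as missing".

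SAP 6.15.4 gives the schedule: "ALSAQ-40 will be measured at Day 0 pre-dose, Day 84 and Day 180". The Protocol's Schedule of Activities has no Screening ALSAQ-40, so Day 0 is the only scheduled pre-dose measurement. SAP 6.2.2 says that baseline "is defined as the last non-missing value (either scheduled, unscheduled or repeat) before the participant receives first Study Injection", without saying whether an item counts as non-missing before or after imputation. SAP 6.2.15 defines change as the post-baseline value minus the baseline value.

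The list of tables in SAP 11 plans each display twice. Items appear in Tables 14.6.4.1 (worst value) and 14.6.4.2 (average), subscales in 14.6.4.3 (worst value) and 14.6.4.4 (average). The title of Table 14.6.4.3, for example, begins "Amyotrophic Lateral Sclerosis Assessment Questionnaire, subscales (worst values imputation". All four use the ITT population, and nothing marks one set as main and the other as sensitivity.

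**The concern.** Worst-value imputation is usually chosen because it is conservative: a participant who skips an item is not credited with doing well on it. For a change score that holds only after baseline. A worst value placed at baseline raises the starting point, so any later real answer looks equal or better. The rule then does the opposite of what it is for.

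The endpoint is change from baseline in quality of life at Days 84 and 180, so baseline enters every result. The eating and drinking subscale has only three items, so each imputed item carries a third of the score. Protocol 5.1 admits only limb-onset disease. It is a reasonable inference, though the documents do not state it, that many participants will have little trouble with eating or speech at entry. Their true item scores would then lie far from the worst value, where the error is largest.

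Separately, with two unranked sets of tables, a reader cannot tell beforehand which one carries the quality-of-life result if they differ.

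**Working it through.** The plan states no figure to reproduce, so the check applies its own scoring formulas.

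**Inputs**
- Subscale score = 100 × (sum of items) / (4k), where k is the number of items. SAP 6.2.11 divides by 12 for 3 items, 28 for 7 and 40 for 10, which implies items scored 0 to 4.
- Direction (assumption): 4 is worst. Protocol 8.3.5.1 orders the responses as "never, rarely, sometimes, often, always, or cannot do at all", describing how often difficulties occur. The documents do not state the coding.
- Change = post-baseline minus baseline (SAP 6.2.15), so a negative change is improvement.
- Planned arms: 12 Engensis, 6 Placebo (Protocol 5.3).

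**Formula.** Suppose m items are missing at Day 0 only, each with true score v at both visits, and imputed as 4 at Day 0. The error added to the participant's change is

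error = −100 × m × (4 − v) / (4k).

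**One missing item (m = 1)**

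| Subscale | v=0 | v=1 | v=2 | v=3 | v=4 |
|---|---|---|---|---|---|
| Eating and drinking (k=3) | −33.3 | −25.0 | −16.7 | −8.3 | 0 |
| Communication (k=7) | −14.3 | −10.7 | −7.1 | −3.6 | 0 |
| 10-item subscales (k=10) | −10.0 | −7.5 | −5.0 | −2.5 | 0 |

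At v = 2 these are 2/12, 2/28 and 2/40, each × 100.

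**Most items the 50% rule allows.** Two of 3 answered is 67% and one is 33%, so at most 1 of 3 can be imputed. Four of 7 is 57% and three is 43%, so at most 3 of 7. Five of 10 is exactly 50%, which is not below the limit, so at most 5 of 10. The error then ranges from 0 to −42.9 on communication (300/7 at v = 0) and from 0 to −50.0 on a 10-item subscale (2000/40 at v = 0).

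**Effect on an arm mean.** One participant with one eating and drinking item missing at v = 2 shifts the mean by 16.7/12 = 1.4 points in Engensis or 16.7/6 = 2.8 in Placebo. At v = 0 the shifts are 33.3/12 = 2.8 and 33.3/6 = 5.6.

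**Four cases on eating and drinking**
- *Missing at Day 0 only, all items truly 2 throughout.* Baseline (2+2+4)/12 = 66.7, later 6/12 = 50.0, change −16.7. Truth: 0.
- *Missing at Day 0 only, all items truly worsening from 1 to 2.* Baseline (1+1+4)/12 = 50.0, later 50.0, change 0.0. Truth: 50.0 − 25.0 = +25.0.
- *Missing at both visits, all items truly 2.* 66.7 − 66.7 = 0; the effect cancels.
- *Missing after baseline only, all items truly 2.* 66.7 − 50.0 = +16.7; the sign reverses.

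**The average rule in the first two cases.** Baseline is 50.0 and 25.0, so the changes are 0.0 and +25.0, both correct. That exactness depends on the items within the subscale being equal. If the answered items are 1 and 1 and the missing one is truly 3, the average rule gives 3/12 = 25.0 against a true 5/12 = 41.7, an error of −16.7 in the baseline. The worst-value rule gives 6/12 = 50.0, an error of +8.3. So the average rule can miss by more in a single case. The difference is that it can miss either way, while a worst value at baseline can only err towards improvement.

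**The case against.** The strongest case against has five parts.

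1. *SAP 6.2.11 never mentions baseline.* This stands as a point of wording: the rule does not exclude baseline, rather than naming it. If non-missing in SAP 6.2.2 is judged before imputation, an unanswered Day 0 item has no baseline in the item table 14.6.4.1 and the artefact does not arise there. The subscale table 14.6.4.3 remains exposed, because the subscale score is built from imputed items and is set to missing only under the 50% rule.
2. *Missing items may be rare.* The ALSAQ-40 is collected electronically (Protocol 8.3.5.1), its form asks participants to try every question (Appendix 7), participants are trained on the device (10.1.6.5), and missing data are raised with sites (10.1.6.3). This bears on likelihood. None of it guarantees completeness, however, and the coordinator's completeness check is described only for the PGIC (8.3.5.2).
3. *A reader might infer a bias in favour of Engensis.* The documents do not support that. The error falls in whichever arm has the missing baseline item. In Placebo it works against Engensis, and one such participant moves that mean twice as far.
4. *A reader might infer that the more favourable set of tables could be quoted.* That is speculation. Both sets are prespecified, use the same population and are labelled by method, and a baseline artefact would show as a gap between Tables 14.6.4.3 and 14.6.4.4.
5. *The endpoint is exploratory and only described, with no test planned.* This stands and limits the importance of the point.

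**Conclusion.** The point holds as a minor one. As written, SAP 6.2.11 allows a worst value to be imputed at Day 0. Where that item is later answered and was truly better than worst, the worst-value subscale table shows improvement that did not occur, or hides real worsening; the item table does the same if the imputed item counts as its baseline. For one missing item the size depends on the true score and the subscale, with the ranges tabulated above; the 50% rule bounds the total.

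This rests on the inferred 0 to 4 coding with 4 worst, and on an item missing at baseline but not later. Without a missing-item rate, no expected bias can be given for either arm or for their difference. The finding is a rule that gives a wrong answer in a definable case, together with the absence of a named main analysis. It is not evidence of a tilt towards the drug or of an intention to choose between tables.

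**What to change.** In SAP 6.2.11:

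- Name the within-subscale average rule (Tables 14.6.4.2 and 14.6.4.4) as the main analysis at all visits.
- Label the worst-value tables (14.6.4.1 and 14.6.4.3) as a sensitivity analysis. In it, worst values are imputed only after baseline, and a missing baseline item takes the within-subscale average, subject to the existing 50% rule.

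The second sentence also settles what a missing Day 0 item contributes, which SAP 6.2.2 leaves open. One consequence should be accepted knowingly: an item missing at both visits no longer cancels in the sensitivity tables. With all eating and drinking items truly 2, it gives 66.7 − 50.0 = +16.7, which is apparent worsening and the direction such an analysis is meant to lean for a participant's own change.

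The cost is two or three sentences, a label on two table titles and a small change to the worst-value derivation. No tables, visits or data are added.
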